## 5.5. Exploratory Endpoints

In addition to the primary and secondary efficacy endpoints, the analyses for exploratory efficacy endpoints will be performed.

- HiSCR
- Lesion Count
- HS-IGA
- IHS4
- HASI
- HSSD pain

### 5.5.1. Endpoint Definitions

#### 5.5.1.1. Hidradenitis Suppurativa Clinical Response (HiSCR)

Please also refer to Section 5.4.2.1 for the definition of the HiSCR50, HiSCR75, and HiSCR90 responder status.

#### 5.5.1.2. Lesion Counts

Details refer to Section 5.4.2.2 for the definition of the lesion counts.

#### 5.5.1.3. International Hidradenitis Suppurativa Severity Score System (IHS4)

Details refer to Section 5.4.2.3.

#### 5.5.1.4. Hidradenitis Suppurativa Investigator's Global Assessment (HS-IGA)

Details refer to Section 5.4.2.4.

#### 5.5.1.5. Hidradenitis Suppurativa Symptom Diary (HSSD)

Details refer to Section 5.4.2.5.

#### 5.5.1.6. Hidradenitis Suppurativa Activity and Severity Index (HASI)

The HASI is a clinician reported outcomes tool that assesses HS severity by incorporating signs of inflammation and surface area involved. The HASI includes 4 domains to assess the severity of HS disease activity: inflammatory color change, inflammatory induration, open skin surface, and extent of tunnels. Each of these variables is scored on a Likert Scale from 0 to 3 (0=none; 1=limited/mild, 2=moderate, 3=severe/extensive) based on the average intensity for each body site. A higher score indicates more severe disease. See Section 10.10 of the JNJ-77474462HDS2001 protocol, Appendix 10 for more details. The HASI score was the total for all body sites and ranged from 0 to 720, with higher scores indicating more severe disease activity.

## 5.5.2. Analysis Methods

The efficacy data from all participants in mFAS will be included and analyzed by study intervention groups from Week 0 through Week 36. The analysis strategy for ICEs and missing data will be handled in the same manner as the secondary endpoints analyses.

All exploratory endpoints over time analyses will be descriptively summarized by treatment groups using descriptive statistics, such as mean, median, standard deviation, interquartile range, minimum and maximum for continuous variables, and counts and percentages for categorical variables.

Additionally, graphical data displays may also be used to summarize the over time data if applicable.

### 5.5.2.1. Analysis Related to HiSCR

- The proportion of participants who achieved HiSCR50 and the proportion of participants who achieved HiSCR50 by baseline Hurley stage (II, III) will be summarized by treatment group over time.
- The proportion of participants who achieved HiSCR75 and HiSCR90 will be summarized by treatment group over time.

### 5.5.2.2. Analyses Related to Lesion Count

- The change from baseline in total AN count will be summarized by treatment groups over time.
- The change from baseline in number of abscesses will be summarized by treatment group over time.
- The change from baseline in number of draining fistulas will be summarized by treatment group over time.
- The change from baseline in number of inflammatory nodules will be summarized by treatment group over time.

### 5.5.2.3. Analysis Related to IHS4

- The change from baseline in IHS4 score will be summarized by treatment group over time.

### 5.5.2.4. Analyses Related to HS-IGA

- The proportion of participants with HS-IGA score of inactive (0), HS-IGA score of inactive (0) or almost inactive (1), and the proportion of participants achieving HS-IGA score of mild activity or better ( $\leq 2$ ) with at least 2-grade improvement from baseline will be summarized by treatment groups over time.

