#### **5.1. Inclusion Criteria**

Each potential participant must satisfy all of the following criteria to be enrolled in the study:

1. Be a male or female 18 (or the legal consent in the jurisdiction in which the study is taking place) years of age or older.
2. Be otherwise healthy on the basis of physical examination, medical history, vital signs, and 12-lead ECG performed at screening. Any abnormalities, must be consistent with the

underlying illness in the study population and this determination must be recorded in the participant's source documents and initialed by the investigator.

3. Have HS for at least 1 year (365 days) prior to the baseline visit as determined by the investigator through participant interview and/or review of the medical history.
4. Have HS lesions present in at least 2 distinct anatomic areas (examples include but are not limited to left and right axilla; or left axilla and left inguocrural fold) at screening and baseline visits.
5. Have Hurley Stage II or Hurley Stage III HS as determined by the investigator at screening and baseline visits.
6. Had an inadequate response to a course of appropriate oral antibiotics for treatment of HS (or demonstrated intolerance to or had a contraindication to oral antibiotics for treatment of their HS) in the investigator's opinion.
7. Criterion modified per Amendment 2.

7.1. Be considered, in the opinion of the investigator, a suitable candidate for adalimumab (HUMIRA®) therapy according to their country's approved HUMIRA product labeling. This criterion only applies to participants enrolling in Part 1 of the study, where adalimumab is one of the possible randomization arms. This criterion does not apply to participants enrolling in Part 2.

8. Have stable HS for at least 60 days prior to the screening visit and at baseline as determined by the investigator through patient interview and/or review of the medical history.
9. Have a total AN count of  $\geq 5$  at the screening and baseline visit.
10. Have screening laboratory test results within the following parameters, if one or more of the laboratory parameters is out of range, a single retest of laboratory values is permitted:
  - a. Hemoglobin  $\geq 10$  g/dL (SI:  $\geq 100$  g/L)
  - b. White blood cells  $\geq 3.5 \times 10^3/\mu\text{L}$  (SI:  $\geq 3.5$  GI/L)
  - c. Neutrophils  $\geq 1.5 \times 10^3/\mu\text{L}$  (SI:  $\geq 1.5$  GI/L)
  - d. Platelets  $\geq 100 \times 10^3/\mu\text{L}$  (SI:  $\geq 100$  GI/L)

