	
 
• Change in number of inflammatory nodules from baseline to Week 16 in Part 1, and at Week 12 in Part 2.
 
• Change of International Hidradenitis Suppurativa Severity Score System (IHS4) score from baseline to Week 16 in Part 1, and at Week 12 in Part 2.
 
• Proportion of participants with HS-Investigator's Global Assessment (HS-IGA) score of inactive (0), almost inactive (1), or mild (2) and with at least 2-grade improvement relative to baseline at Week 16 in Part 1, and at Week 12 in Part 2.
 
• Proportion of participants with HS-IGA score of inactive (0) or almost inactive (1) at Week 16 in Part 1, and at Week 12 in Part 2 among participants with HS-IGA score of moderate (3) or severe (4) at baseline.
 

 
• To characterize additional patient-reported outcome efficacy measures of bermekimab in participants with moderate to severe HS.
 
	
 
• Change in Dermatology Life Quality Index (DLQI) score from baseline to Week 16 in Part 1, and at Week 12 in Part 2.
 
• Change in Hidradenitis Suppurativa Symptom Diary (HSSD-24h) score from baseline to Week 16 in Part 1, and at Week 12 in Part 2.
 
• Change in pain scale score of HSSD-24h from baseline to Week 16 in Part 1, and at Week 12 in Part 2.
 
• Change in itch scale score of HSSD-24h from baseline to Week 16 in Part 1, and at Week 12 in Part 2.
 

 
• To assess the safety and tolerability of bermekimab in participants with moderate to severe HS.
 
	
 
• Number/proportion of participants with treatment-emergent adverse events (TEAEs).
 
• Number/proportion of participants with treatment-emergent serious adverse events (SAEs).
 
• Number/proportion of participants with abnormal safety laboratory values.
 

 
• To evaluate the pharmacokinetics (PK) and immunogenicity of bermekimab in participants with moderate to severe HS.
 
	
 
• Bermekimab concentration will be summarized for treated participants over time.
 
• The incidence of antibodies to bermekimab will be summarized.
 

Exploratory	

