
 
• To evaluate the clinical efficacy of bermekimab in participants with moderate to severe HS.
 
	
 
• Change of Hidradenitis Suppurativa Area and Severity Index (HASI) score from baseline to Week 16 in Part 1, and at Week 12 in Part 2.
 
• Proportion of participants achieving HiSCR50, HiSCR75, and HiSCR90 over time.
 

Objectives	Endpoints
	
 
• Change from baseline in AN count over time.
 
• Proportion of participants achieving at least 50%, 75%, 90%, and 100% reduction in total AN count over time.
 
• Change in the number of abscesses, draining fistulas, and inflammatory nodules from baseline over time.
 
• Change of HASI score from baseline over time.
 
• Change of IHS4 score from baseline over time.
 
• Proportion of participants with HS-IGA score of inactive (0), almost inactive (1), or mild (2) and with at least 2-grade improvement relative to baseline over time.
 
• Proportion of participants with HS-IGA score of inactive (0) or almost inactive (1) over time among participants with HS-IGA score of moderate (3) or severe (4) at baseline.
 
• Change in high-sensitivity C-reactive protein (hs-CRP) from baseline to Week 16 in Part 1 and from baseline to Week 12 in Part 2.
 

 
• To characterize additional patient-reported outcome efficacy measures of bermekimab in participants with moderate to severe HS.
 
	
 
• Change in DLQI score from baseline over time.
 
• Change in Hidradenitis Suppurativa Symptom Diary (HSSD-24h) score from baseline over time.
 
• Change in pain scale score of HSSD-24h from baseline over time.
 
• Change in itch scale score of HSSD-24h from baseline over time.
 
• The distribution of the Patient Global Impression of Change (PGIC) of HS at Week 16 in Part 1, and at Week 12 in Part 2.
 
• The distribution of the Patient Global Impression of Severity (PGIS) of HS at Week 16 in Part 1, and at Week 12 in Part 2.
 
• Change in PROMIS 29 total score and sub-scores from baseline to Week 16 in Part 1, and at Week 12 in Part 2 and over time.
 
• Change in Hidradenitis Suppurativa Symptom Diary (HSSD-7d) score from baseline over time.
 

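### SAP 5.5.2.4 summarises HS-IGA 0/1 in all mFAS participants, although SAP 1.1 and the protocol define that endpoint only for baseline HS-IGA 3 or 4

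*SAP*

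**What the plan says.** SAP 1.1 lists an exploratory endpoint that follows HS-IGA 0 or 1 "over time among participants with HS-IGA score of moderate (3) or severe (4) at baseline". It also lists a secondary Week 16 version, again "among participants with HS-IGA score of moderate (3) or severe (4) at baseline". Protocol Section 3 carries the same restriction for both, and protocol 9.4.2.2 repeats it for the planned Week 16 comparison.

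The analysis text differs. SAP 5.5.2.4 begins "The proportion of participants with HS-IGA score of inactive (0), HS-IGA score of inactive (0) or almost inactive (1" and names no baseline subgroup. The second proportion in that run, "HS-IGA score of inactive (0) or almost inactive (1", is the one at issue. SAP 5.5.2 sets the population: "The efficacy data from all participants in mFAS will be included and analyzed by study intervention groups from Week 0 through Week 36". On the type of analysis it says: "All exploratory endpoints over time analyses will be descriptively summarized by treatment groups".

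The same bullet in 5.5.2.4 adds a third proportion, HS-IGA of 2 or lower, which carries its own condition: "with at least 2-grade improvement from baseline will be summarized by treatment groups over time".

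On entry, protocol 5.1 sets severity by Hurley stage ("Have Hurley Stage II or Hurley Stage III HS as determined by the investigator at screening and baseline visits") and by an AN count of at least 5. Neither 5.1 nor 5.2 sets a minimum HS-IGA.

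**The concern.** The proportion that 5.5.2.4 would produce is not the endpoint that 1.1 defines. The restriction to baseline 3 or 4 makes a score of 0 or 1 mean an improvement of at least two grades. Without it, the same score can mean a one-grade change (from 2) or no change at all (from 0 or 1).

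The SAP contains no other analysis that would supply the defined endpoint. SAP 5.4.3 and 5.4.4 keep only the HS-IGA response that requires a two-grade improvement, so the Week 16 HS-IGA 0/1 endpoint listed as secondary in 1.1 has no analysis there. A reader of the study report who looks for HS-IGA 0/1 would find only the unrestricted version, under a label that the objectives table attaches to a restricted one.

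**Working it through.** The documents state no figure for HS-IGA 0/1, so there is none to reproduce. The check is a comparison of text, followed by an illustration on assumed inputs.

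**Does anything restore the restriction?**
- SAP 5.5.1.4 refers to 5.4.2.4 for the definition. That section describes the scale and the region scored; it sets no denominator.
- SAP 5.5.2 states the population as all of mFAS. Section 4 defines mFAS by dosing and by whether the visit could have been reached before the termination decision, not by baseline severity.
- SAP Appendix 2 says in general terms that analyses were reduced after termination. Dropping analyses does not declare a changed denominator in one that was kept.

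**Can baseline scores of 0 to 2 occur?** Yes. No inclusion or exclusion criterion refers to a minimum HS-IGA. Against that, SAP 5.4.2.4 and protocol 8.1.1 have the investigator score the region with the most severe activity at baseline, so a baseline of 0 or 1 is allowed but unlikely.

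**Which proportions in the bullet are exposed?** HS-IGA 0 and HS-IGA 0/1. The third proportion cannot count anyone starting at 0 or 1, because a two-grade fall from there is impossible.

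**Illustration 1: baseline 0/1.** Let p be the response rate among baseline 3 or 4. Let f be the share of each arm that starts and stays at 0/1 with no intercurrent event of type 1 or 2. Assume no one starts at 2.
- Unrestricted rate = (1 − f)p + f
- Unrestricted difference = (1 − f) × restricted difference

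With assumed rates of 20% and 40%, and the planned 50 per arm used only to turn shares into counts:

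| f | Participants per arm | Lower-rate arm | Higher-rate arm | Difference (points) |
|---|---|---|---|---|
| 0% | 0 | 20.0% | 40.0% | 20.0 |
| 2% | 1 | 21.6% | 41.2% | 19.6 |
| 4% | 2 | 23.2% | 42.4% | 19.2 |
| 10% | 5 | 28.0% | 46.0% | 18.0 |
| 20% | 10 | 36.0% | 52.0% | 16.0 |

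At f = 10%: 0.9 × 20 + 10 = 28.0; 0.9 × 40 + 10 = 46.0; 46.0 − 28.0 = 18.0. With the restriction in place the difference is 20.0 in every row.

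If k such participants fall in one arm only, that arm moves by k(1 − p)/50. At p = 20% this is 1.6 points for one participant and 3.2 points for two, with no treatment effect behind it.

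**Illustration 2: baseline 2.** Let g be the share starting at 2, and q their response rate. The arm rate is (1 − g)p + gq. With assumed p = 20% and q = 40%, shares of 10%, 20% and 30% give 22%, 24% and 26%. The between-arm difference, for equal g in both arms, is (1 − g) × (difference among baseline 3 or 4) + g × (difference among baseline 2). It shrinks if the baseline-2 difference is the smaller of the two and grows if it is the larger. The documents do not say which.

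**The case against.** The strongest reply is that 5.5.2.4 is shorthand. It packs three proportions into one bullet, and the population statement in 5.5.2 is a general one for all exploratory endpoints, so a programmer might carry over the subgroup from 1.1. This is possible, but the text does not say it. The bullet also includes HS-IGA 0 alone, which 1.1 does not list, so it is not simply restating 1.1. Even on this reading the SAP supports two denominators for one reported proportion.

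The second reply is that little depends on it. That stands. The summary is descriptive, with no test. The SAP was written after the futility criterion was met and the study terminated. The HS-IGA endpoint that is still tested at Week 16 requires a two-grade improvement. Baseline HS-IGA is to be summarised by treatment group (SAP Appendix 3), and the over-time summaries start at Week 0, so a careful reader could see whether many participants began low.

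A reader might also infer that participants starting at 0/1 are in fact being counted as responders, that every arm is inflated by some 5 to 10 points, and that the treatment contrast is diluted throughout. The documents do not support this. They give no baseline HS-IGA distribution. Scoring the most severe region in Hurley II or III participants with an AN count of at least 5 makes baseline 0/1 unlikely. Dilution follows only for participants who start and stay at 0/1; for those starting at 2, probably the larger group, the direction is open.

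**Conclusion.** The mismatch holds on the text: 5.5.2.4 as written does not produce the endpoint defined in SAP 1.1 and protocol Section 3, the change is undeclared, and no other HS-IGA 0/1 analysis exists in the SAP.

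The numerical effect is conditional and unknown. It is zero if every participant starts at 3 or 4, and may be near zero for baseline 0/1. The fall from 20 to 18 points rests on three assumptions: a 10% share in each arm that starts and stays at 0/1, true rates of 20% and 40%, and no participants starting at 2.

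The primary endpoint, HiSCR50, is built from lesion counts and does not use HS-IGA. The primary result, type I error and power are therefore untouched. This is a minor point about the correctness of one exploratory summary.

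**What to change.** In SAP 5.5.2.4, restrict the HS-IGA 0/1 summary to mFAS participants with a baseline HS-IGA of 3 or 4, and show that denominator at each visit. If the all-mFAS version is also wanted, declare it in Appendix 2 as a departure from the protocol and present it beside the restricted one.

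The cost is one clause and one denominator filter. Baseline HS-IGA is already collected at Week 0 under the protocol's Schedule of Activities, so no new data are needed.

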### 5.5.2.5. Analyses Related to HASI

- The change from baseline in HASI score over time will be summarized by treatment groups over time.

### 5.5.2.6. Analyses Related to HSSD

- The change from baseline in HSSD pain score (24 hours recall) will be summarized over time.
- The change from baseline in HSSD pain score (7 days recall) will be summarized over time.

## 5.6. Safety Analyses

All safety analyses will be performed using safety analysis set based on actual intervention received. No formal statistical comparison is planned.

For all continuous safety variables, descriptive statistics by intervention group will include the N, mean, standard deviation, median, minimum, and maximum. Categorical variables will be summarized by intervention group using frequency counts and percentages.

### 5.6.1. Extent of Exposure

The number and percentage of participants who receive study intervention (placebo, bermekimab, and adalimumab) will be summarized. The number and percentage of participants will also be summarized by visit.

Descriptive statistics will be presented by intervention group for the following parameters:

- Number of administrations
- Cumulative total dose
- Duration of study intervention (weeks)

Study intervention duration is defined as  $(\text{date of last dose of study intervention} - \text{date of first dose of study intervention} + 1) / 7$ .

### 5.6.2. Adverse Events

The verbatim terms used in the CRF by investigators to identify adverse events will be coded using the Medical Dictionary for Regulatory Activities (MedDRA). Any AE occurring at or after the initial administration of study intervention is considered to be treatment emergent. If the event occurs on the day of the initial administration of study intervention, and either event time or time of administration are missing, then the event will be assumed to be treatment emergent. If the event date is recorded as partial or completely missing, then the event will be considered to be treatment emergent unless it is known to be prior to the first administration of study intervention based on partial onset date or resolution date. All reported treatment-emergent adverse events will be included in the analysis. For each adverse event, the number and percentage of participants who experience at least 1 occurrence of the given event will be summarized by intervention group.

Summary tables will be provided for treatment-emergent adverse events:

- AEs

- 
- Serious AEs (SAEs)
  - AEs leading to discontinuation of study intervention
  - AEs of severe intensity
  - AEs related to study intervention
  - AEs of injection site reaction

In addition to the summary tables, listings will be provided for participants who:

- Had SAEs
- Had AEs leading to discontinuation of study intervention
- Had AEs of severe intensity
- Had anaphylactic or serum sickness-like reactions

Since safety should be assessed relative to exposure and follow-up, most AE summary tables will include average weeks of follow-up and average number of study agent administrations for each intervention group.

A listing of participants who died will be provided.

### **5.6.3. Additional Safety Assessments**

#### **5.6.3.1. Clinical Laboratory Tests**

Clinical laboratory tests will be displayed for the participants included in the safety analysis set.

Descriptive statistics of change from baseline through Week 36 will be summarized for selected chemistry, and hematology tests and displayed by intervention group.

- **Hematology** will include but are not limited to the following: Basophils, Eosinophils, Hemoglobin, Lymphocytes, Monocytes, Neutrophils, Platelets, WBC, CRP and ESR.
- **Chemistry** will include but are not limited to the following: ALT, AST, Albumin, Alkaline Phosphatase, Bicarbonate (CO2), Calcium, Chloride, Creatinine, GGT, Glucose, Potassium, SGOT, SGPT, Sodium, Total Bilirubin, Total Protein, Urea Nitrogen.

Applicable laboratory results will be graded according to National Cancer Institute's Common Terminology Criteria for Adverse Events (NCI-CTCAE). Participants with toxicity grades  $\geq 2$  will be listed.

## 5.7. Other Analyses

### 5.7.1. Pharmacokinetics

All PK analyses will be performed on the PK analysis set, defined as participants who have received at least 1 dose of bermekimab and have at least 1 valid blood sample drawn for PK analysis. Participants will be analyzed according to the treatment groups they actually received. No imputation for missing concentration data will be performed.

Blood samples for measuring bermekimab concentrations will be collected from all participants at the specified visits as shown in the schedule of activities in the protocol. Samples will also be collected at the final visit from participants who terminate study participation early. Samples must be collected before study agent administration at visits when a study agent administration is scheduled.

Bermekimab concentrations will be summarized using descriptive statistics, including n, arithmetic mean, SD, coefficient of variation (%CV), median, interquartile range, range (minimum and maximum), by treatment group at each PK sampling time where appropriate. PK data may be displayed graphically. The following analyses will be performed as appropriate:

- Summary of bermekimab concentrations at each visit by treatment group.
- Proportion of participants without detectable bermekimab concentration (below the lower limit of quantification) at each visit by treatment group.
- Summary of bermekimab concentrations at each visit by treatment group and baseline body weight ( $\geq 95$  or  $< 95$  kg).
- Summary of bermekimab concentrations at each visit by treatment group and baseline Hurley stage status (II, III).
- Plot of median (IQ) bermekimab concentrations over time by treatment group.
- Plot of median (IQ) bermekimab concentrations over time by baseline body weight and treatment group.

Unless otherwise specified, the following data handling rules will apply to PK analyses:

- All concentration summaries for a particular timepoint will include data obtained from treated participants at the timepoint of interest without imputing any missing data. A concentration not quantifiable (below the lower limit of quantification) will be treated as 0 in the summary statistics and shown as the lower limit of quantification ( $< \text{LLOQ}$ ) in the data listings.
- The data from a participant who meets 1 of the following dosing deviation criteria (if applicable) will be excluded from the by-visit data analyses from that point onwards:
  - Discontinue bermekimab administrations.
  - Skipped a bermekimab administration.
  - Received an incomplete/ incorrect dose (if applicable).
  - Received an incorrect study agent (if applicable).

- Received an additional bermekimab dose.

In addition, if a participant has an administration outside of dosing windows ( $\pm 3$  days from scheduled visit from Week 0 through Week 32), the concentration data collected at and after that visit will be excluded from the by-visit data analyses. Additional exclusions for incongruous PK data to be implemented based on Janssen SOP-07948. All participants and samples excluded from the analysis will be clearly documented in the Clinical Study Report.

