The weekly dose frequency was selected based on bermekimab half-life ( $T_{1/2}$ ). Bermekimab  $T_{1/2}$  was estimated to be approximately 1 week so that a weekly dose regimen would maintain adequate drug exposure over the entire dosing interval. Given that the initial intensive treatment with weekly doses of bermekimab for 12 weeks is expected to reduce participants' inflammatory burden, a less frequent dose regimen may be sufficient for maintenance therapy. In addition, less frequent dosing interval will decrease participant burden. Therefore, instead of testing 700 mg qw and 350 mg qw regimens in Part 2, bermekimab 1050 mg qw→q2w (starting at Week 12) or 700 mg qw→q2w (starting at Week 12) regimens will be implemented. Whether 700 mg qw→q2w will be included in Part 2 will be based on interim analysis results from Part 1. Details will be described in the interim analysis plan.

Bermekimab was well-tolerated in the 2018-PT045 study (400 mg SC qw for 13 weeks) with no safety concerns. In the completed Phase 2 AD and HS studies 77474462HDS2002 (NCT04019041) study and 77474462ADM2002 (NCT04021862), bermekimab 800 mg at Week 0, 1 followed by 400 mg qw or 400 mg q2w were both safe and well-tolerated in participants with HS through Week 36. The highest dose of bermekimab studied was 7.5 mg/kg IV q2w for 12 weeks in HS (10 participants; [Kanni, 2018](#)), with no safety concerns. The 7.5 mg/kg IV dose is equivalent to a 1125 mg SC dose for a 90 kg (average body weight of HS patients, 77474462HDS2002) individual assuming an SC bioavailability of 60%. Based on the preliminary PK simulation, the median  $C_{max}$  for the highest dose of 1050 mg SC qw would be lower (0.83-fold) than that for the 7.5 mg/kg IV q2w dose regimen while the median  $AUC_{2weeks}$  would be higher (1.85-fold) than that for the 7.5 mg/kg IV q2w dose regimen. Given the safety margins calculated based on predicted human PK exposure at 1050 mg SC qw (ie., 40-fold for  $C_{max,ss}$  and 33-fold for  $AUC_{1week,ss}$ ) relative to that at monkey NOAEL (300 mg/kg SC qw, Section 2.2), dose

regimens of up to 1050 mg SC qw proposed in this Phase 2 study would have adequate safety margins.

To actively monitor unblinded safety data on ongoing basis, an independent DMC will be commissioned in this study (Section 9.6, Data Monitoring Committee).

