#### **Group 1: Placebo**

Participants will receive 4 placebo SC injections at Week 0. Participants will receive 3 placebo SC injections at Week 1 and every week thereafter through Week 15. At Week 16, participants will cross over to receive 3 bermekimab 350 mg SC injections weekly through Week 31.

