## INTERVENTION GROUPS AND DURATION

### Part 1:

#### Group 1: Placebo

Participants will receive 4 placebo SC injections at Week 0. Participants will receive 3 placebo SC injections at Week 1 and every week thereafter through Week 15.

At Week 16, participants will cross over to receive 3 bermekimab 350 mg SC injections weekly through Week 31.

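### The PK dosing-window rule in SAP 5.7.1 is not limited to bermekimab, so one out-of-window placebo injection before the Week 16 crossover removes a Part 1 placebo participant's later bermekimab concentrations from the by-visit analyses

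*SAP*

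**What the plan says.** SAP 5.7.1 gives two exclusion rules for the by-visit concentration analyses.

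- **Dosing-deviation list.** Data from a participant who meets any listed deviation "will be excluded from the by-visit data analyses from that point onwards". The items for discontinued, skipped and additional doses name the drug, for example "Skipped a bermekimab administration". The items for an incomplete or incorrect dose and for an incorrect agent do not, but they apply only where applicable.
- **Window rule.** This is added to the list and is triggered "if a participant has an administration outside of dosing windows", defined as 3 days either side, "days from scheduled visit from Week 0 through Week 32". The consequence is that "the concentration data collected at and after that visit will be excluded from the by-visit data analyses". It names no drug.

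Neither rule says when, or whether, a participant re-enters.

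For the Part 1 placebo group, SAP 1.2 states: "Participants will receive 3 placebo SC injections at Week 1 and every week thereafter through Week 15". Protocol 6.1 continues: "At Week 16, participants will cross over to receive 3 bermekimab 350 mg SC injections weekly through Week 31". SAP Section 4 defines the PK analysis set as participants with at least one bermekimab dose and at least one valid PK sample, so placebo participants can join it once they have crossed over.

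**The concern.** The window rule starts at Week 0, and for the placebo group Weeks 0 to 15 contain no bermekimab. Read literally, an injection that contains no bermekimab decides whether bermekimab concentrations measured weeks later are summarised. The exclusion then has no pharmacokinetic purpose.

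Every concentration output listed in SAP 5.7.1 is by visit or over time, so an excluded participant leaves all of those summaries and plots. At stake is the size and make-up of the crossover group in a descriptive secondary endpoint, namely bermekimab concentration over time in treated participants. Protocol 9.4.4 plans that summary by visit and treatment group and states no dosing-deviation exclusion. SAP Appendix 2 says only that the PK analyses were reduced.

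**Working it through.** The plan states no figure for this rule, so there is nothing to reproduce. The check is a reading of the text, followed by two calculations for scale.

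**1. Does the rule reach placebo injections?**
- Trigger: any administration, Weeks 0 to 32 (SAP 5.7.1).
- Placebo group: placebo at Weeks 0 to 15, bermekimab from Week 16 (SAP 1.2, Protocol 6.1).
- Visit dates are counted from the Week 0 administration (Protocol 1.3.1, footnote b). Week 0 cannot be out of window, which leaves 15 placebo visits, Weeks 1 to 15.
- Scheduled PK samples after crossover: Weeks 20, 24, 28, 32 and 36 (Protocol 1.3.3). The Week 16 sample is taken before the first bermekimab dose.

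A placebo injection given 4 days late at Week 5, for example, excludes all five of those samples. One given more than 3 days early does the same. A skipped placebo injection does not, because the skip item names bermekimab. Neither document limits the window rule elsewhere.

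**2. How many placebo participants could this affect?** The documents give no rate of out-of-window injections, so the rate p per visit is assumed, independent between visits and the same for everyone. The share with at least one in 15 visits is 1 − (1 − p)^15.

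| Assumed p | Share excluded before any bermekimab |
|---|---|
| 1% | 1 − 0.99^15 = 14% |
| 2% | 1 − 0.98^15 = 26% |
| 5% | 1 − 0.95^15 = 54% |

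Because (1 − p)^15 is convex in p, the share is lower if the same mean rate is concentrated in a few participants. For a given mean rate, these figures are closer to upper bounds.

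**3. How long does a real bermekimab deviation matter?** Protocol 4.3 says that the half-life "was estimated to be approximately 1 week so that a weekly dose regimen would maintain adequate drug exposure over the entire dosing interval". Take one compartment, a 1-week half-life, weekly dosing and instantaneous absorption (a simplification). The trough at week t is then the sum of 0.5^(t − s) over dose times s before t.

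- With no deviation, the trough at Week 5 is 0.5 + 0.25 + 0.125 + 0.0625 + 0.03125 = 0.96875.
- Skipping the Week 4 dose removes 0.5 at Week 5: −0.5/0.96875 = −52%. At Week 9 it removes 0.5^5 = 0.03125 from about 0.998: −3.1%.
- Giving the Week 4 dose 4 days late multiplies its contribution by 2^(4/7) = 1.486. At Week 5 the change is 0.5 × 0.486/0.96875 = +25%, and at Week 9 about +1.5%.

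A placebo injection contributes nothing to this sum, whenever it is given.

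**The case against.** The strongest reply is that the rule is narrower than it looks and partly a legitimate choice. Several parts of that reply stand.

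- **The data are not lost.** A reader might infer that the concentrations disappear from the study. They leave only the by-visit analyses. Data listings remain, population PK has its own analysis plan (Protocol 9.4.4), and SAP 5.7.1 requires excluded participants and samples to be documented in the clinical study report.
- **Permanent exclusion is defensible.** A reader might infer from the 1-week half-life that exclusion without re-entry is itself an error. Describing concentrations under the nominal regimen up to the first deviation is a clear prespecified choice for a descriptive endpoint. A fixed washout would be a trade-off, because troughs after late or extra doses sit above steady state and those after skipped doses sit below it.
- **There is no link to futility.** A reader might infer that the exclusion weakens the check on whether exposure was adequate in a trial stopped for futility. No section gives the Week 16 to 36 by-visit summaries that role. SAP 5.8 bases the interim decision on HiSCR50 at Week 16, with PK used to inform Phase 2b regimens. Concentrations after crossover cannot explain a Week 16 result.
- **The numbers are assumptions.** Dosing is on site, and Protocol 6.4 makes site personnel responsible for compliance. The 3-day margin on either side is also wide for a weekly schedule, so the rule does not demand perfect attendance. Extending the arithmetic to Week 31 in the bermekimab arm would ignore the early termination.

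None of this answers the placebo point. An interest in nominal dosing cannot justify excluding bermekimab concentrations because of a placebo injection.

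**Conclusion.** The point holds as a defect of wording with a definite consequence. As written, one placebo injection more than 3 days off schedule in Weeks 1 to 15 removes a Part 1 placebo participant's Week 20 to 36 concentrations from every by-visit summary and plot in SAP 5.7.1. This conclusion rests on the text alone.

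The 14%, 26% and 54% rest on assumed, independent and equal per-visit rates. They show scale and do not estimate what happened in this trial. They apply to placebo participants who reach crossover, and the termination decision of 14 October 2022 means that this may be fewer than planned.

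The half-life calculation shows that the effect of one bermekimab deviation on troughs largely fades within about 5 weeks. That supports a sensitivity summary, but it does not make the permanent exclusion wrong. Primary efficacy and the futility decision are untouched.

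**What to change.** In SAP 5.7.1:

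1. Change the trigger of the window rule to a bermekimab administration, counted from the participant's first bermekimab dose (Week 16 for the Part 1 placebo group).
2. Add one by-visit concentration summary without the dosing-deviation exclusions, as a sensitivity analysis. The permanent exclusion may remain the main rule.

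The first change is a few words and a date condition in the PK programming. The second costs one extra descriptive table. Neither needs new data.
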